All study procedures will be conducted virtually by study staff over Partners-approved channels of communication. We expect to consent and evaluate for eligibility up to 160 inpatients at the Gavin CSS in order to achieve our projected randomized sample size of 88 patients with OUD to have 68 participants complete the 10-day trial. Participants will be randomized in a 1:1 ratio to pramipexole 0.25–0.5 mg or equivalent placebo for 10 days.

Eligible patients will be randomized to 10 days of pramipexole or placebo after an initial 3-day screening period to ensure the stability of RLS and opioid withdrawal symptoms. Participants will complete 5 study visits mainly over video or phone: initial screening visit (V1), consent/screening visit (V2), randomization visit (V3), Day 3 interim visit (V4), and an end-of-treatment visit (V5).

Pramipexole will be started at 0.25 mg nightly or identical placebo for the first 3 days. If this dose is well tolerated but not effective after 3 days of treatment, as determined by the day 3 visit, two tablets per night will be given. Note that this means some patients will receive two doses of placebo tablets per night.

All of the participants in this trial are diagnosed with OUD, a condition that may be associated with increased risk of COVID-19-related complications. Thus, considering the safety and psychological wellbeing of our participants, most interactions between participants and study staff will occur remotely. Some visits may take place in person at the Gavin Foundation if virtual visits are considered to be an excess burden to participants or study staff. Necessary precautions, in accordance with MGH policy, will be in place. For the remote visits, research staff will follow the Partners Healthcare requirements for using the appropriate virtual tools: visits will occur via video (Microsoft Teams or other Partners-approved programs) or telephone. A study physician will remain on call in case there any emergent medical or psychiatric issues.

The Gavin Foundation CSS will be provided with a computer that will be used for questionnaires and study visits. This computer will meet all MGB security standards. The Gavin Foundation staff

has agreed to place this computer in a location where participants can complete questionnaires and meet with MGH study staff privately.

V. OVERVIEW OF STUDY PROCEDURES

PRE-SCREEN (VISIT 1):

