Screening Run-In (3 days): The participant will receive daily email links to an online sleep diary and three questionnaires: the IRLS subscale, SOWS, and an opioid craving visual analog scale. Baseline subjective sleep measures will be determined from this 3-day period.

RANDOMIZATION VISIT (VISIT 3) AND TREATMENT PERIOD:

A more thorough medical history will be collected at the Randomization Visit, along with demographic information. At this visit, the 3-day sleep diary and questionnaire results will be reviewed for final eligibility before the participant is randomized to treatment.

Eligible participants will be randomized in a 1:1 ratio to 10 days of placebo or pramipexole. Pramipexole will be started at 0.25 mg nightly for the first 3 days. On day 3, a study physician will call the participant over the phone or on video to inquire about efficacy and adverse events (Visit 4). Visit 4 may occur on day 4 or 5 if the study physician is unable to meet on day 3. If the 0.25-mg dose is well tolerated but not effective, the dose can be increased to 0.5 mg.

Participants will receive medication from the Gavin Foundation staff and will complete the online sleep diary and questionnaires every day (see the Table of Procedures below for the exact schedule). Gavin Foundation staff will direct participants to the secure computer on which they can complete the sleep diary and questionnaires.

FINAL STUDY VISIT (VISIT 5):

On Day 10, participants will meet with a study physician. The physician will assess the participant on the Clinical Global Impression-Improvement (CGI-I) scale and will also inquire about any adverse events experienced. If a participant is discharged from the Gavin Foundation CSS before Day 10, study staff will attempt to perform Visit 5 before his or her departure from the facility.

Compensation:

Participants will be remunerated. Any earnings will be loaded onto a debit card, which will be given to the participant when he or she leaves the Gavin Foundation CSS.

Participants will be paid based on completion of sleep diaries and questionnaires after receiving study drug.

The payment schedule is as follows:

- \$5/day for filling out diaries and questionnaires on the 10 days on study drug
- \$25 for fully completing the study (i.e. spending 10 days on the study drug and completing 10 days of diary entries)

The total possible compensation is \$75.

[figure not shown]

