All study medication dispensed by the investigators or designee will be accounted for throughout the study. Information about participant dosing and compliance will be recorded in the participant's clinical records. Participants who are noncompliant with medications (according to clinical records and diaries) may be removed from the study at the discretion of the investigators.

Randomization:

Randomization will be used to avoid bias in the assignment of participants to treatment, to increase the likelihood that known and unknown participant attributes (e.g., demographics and baseline characteristics) are evenly balanced across treatment groups, and to enhance the validity of statistical comparisons across treatment groups. Blinded treatment will be used to reduce potential bias during data collection and evaluation of clinical endpoints.

At the initial visit, participants will be assigned a 3-digit participant number, in ascending sequential order beginning with 001. The participant number will be retained by the participant for

the duration of the study. The MGH Clinical Trials Pharmacy will provide and maintain randomization and blinding. Participants will be randomized to receive either pramipexole or placebo in a 1:1 ratio. Participants and investigators will be blinded to treatment assignment. Participants will be randomized sequentially as they qualify for the study.

Blinding:

The randomization code will be maintained by the MGH Clinical Trials Pharmacy and will not be revealed to study participants, investigators or blinded clinical staff until all participants have completed and the database has been finalized.

Under normal circumstances, the blind should not be broken. The blind should be broken only if specific treatment would be dictated by knowing the treatment status of the participant. Individual code breaks by the investigators will normally result in withdrawal of the participant from the trial. The date, time and reason for the unblinding must be documented in the study files.

VII. RISKS AND DISCOMFORTS

Medication Side Effects and Adverse Events:

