The following adverse events have been reported more frequently during use of pramipexole in restless legs syndrome patients than under placebo: nausea and fatigue. Less common adverse events were constipation, dry mouth, diarrhea, and upper respiratory tract infections. A few rare, but serious adverse events have been linked to pramipexole, including impulse control disorders, confusion, and hallucinations. Note that some of these symptoms overlap with those of opioid withdrawal.

Participants will be assessed for depression and anxiety during the study, using the Patient Health Questionnaire (PHQ-9) and the General Anxiety Disorder 7-item scale (GAD-7) (Kroenke et al., 2001, Spitzer et al., 2006).

All adverse events that occur between the first study-related procedure and within 30 days of the last dose of study medication will be reported. Adverse events will be reported to the Partners IRB according to guidelines.

Participants will be at Gavin CSS and monitored by Gavin Foundation staff who will report and record symptoms including adverse events.

Participants will be asked about adverse events each day by Gavin Foundation staff. Participants should report any adverse events voluntarily or in response to general, non-directed questioning (e.g., "How has your health been since the last visit?). Participants will also be asked about adverse events at the Day 3 (Visit 4) call and at the Final Study Visit (Visit 5).

All adverse events, regardless of seriousness, severity, or presumed relationship to study therapy, must be recorded using medical terminology in the participant's study documents. Whenever possible, diagnoses should be given when signs and symptoms are due to a common etiology (e.g., cough, runny nose, sneezing, sore throat, and head congestion should be reported as "upper

respiratory infection"). A study physician must document his/her opinion concerning the relationship of the adverse event to the study medication.

VIII. POTENTIAL BENEFITS

Participants may not benefit from taking part in this study. Some participants will receive pramipexole, which may help with their restless legs syndrome symptoms. Participants may benefit from the sleep diaries, review of their symptoms, and discussions with the study doctor. Participants may also be paid for their participation in this study.

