This research has potential benefits to society: this study may help other people with OUD and RLS symptoms by adding to the knowledge about this drug, and whether it is a beneficial treatment.

IX. BIOSTATISTICAL ANALYSIS

Analysis of all study data will be conducted by [name], [name], and [name] or another statistician at Partners Healthcare hospitals. All study personnel and participants will remain blinded to treatment assignment, including staff entering study data. Only the hospital Research Pharmacist who generates the randomization code and [name] who will conduct the interim analysis will be unblinded to treatment assignment. The final database will not be unblinded to study staff until all study data are complete and a medical and scientific review by [name] is conducted.

Overview of analytic plan:

We will conduct an interim analysis to probe the futility of the study. We will use the data obtained to date to estimate the effect of randomized treatment group on two outcomes (primary outcome: IRLS score; secondary outcome: SOWS). We will then use this estimate to determine the sample size necessary to detect this effect. To protect the blind, a statistician ([name]) who is not involved in the day-to-day running of the study, will conduct the analyses.

We will perform both intent-to-treat (ITT) analyses (including all patients who received one dose of study medication and complete one assessment post-randomization) and per protocol analyses (including participants with 10 days of evaluable data). Distributions of the outcomes will be examined and data transformation will be applied to satisfy the normality assumptions.

We will analyze data in several ways: comparison of change from randomization to end of Day 5; comparison of change from randomization to end of Day 10; and using all daily values (i.e., longitudinal analyses). The two groups are drug and placebo.

Study endpoints:

The primary outcome (IRLS score) and all secondary and exploratory measures are continuous variables. We will modify the IRLS in two ways: (i) only the symptoms subscale will be employed (only items 1, 2, 4, 6, and 8 will be included); and (ii) the questions will be modified to include symptoms for only the last 24 hours rather than for the previous 7 days. Primary

analyses will focus on the difference in the change in IRLS subscale from randomization to Day 5 and from randomization to Day 10 between the two groups.

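### Noncompliant patients may be removed from the study, not only from drug, so ITT patients can lack the Day 5 or Day 10 IRLS and SOWS values that the t-tests need

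*Combined protocol and SAP*

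**What the plan says.** Section VI, Study Medication Accountability and Compliance: "Participants who are noncompliant with medications (according to clinical records and diaries) may be removed from the study at the discretion of the investigators". Section VI, Blinding: "Individual code breaks by the investigators will normally result in withdrawal of the participant from the trial". Neither sentence says that questionnaires continue afterwards, and no other section does.

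Section IX, Overview of analytic plan, defines the ITT set as "including all patients who received one dose of study medication and complete one assessment post-randomization". The Primary and Secondary analysis paragraphs then apply two-sample t-tests to the change in IRLS subscale and in SOWS to Day 5 and to Day 10, followed by linear mixed-effects models on the repeated values. No imputation or other missing-data rule is given for the t-tests.

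The one early-exit provision concerns discharge (section V, Final Study Visit): "If a participant is discharged from the Gavin Foundation CSS before Day 10, study staff will attempt to perform Visit 5".

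Section V, Compensation, pays $5 a day "for filling out diaries and questionnaires on the 10 days on study drug" and $25 "for fully completing the study (i.e. spending 10 days on the study drug and completing 10 days of diary entries".

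**The concern.** Removal for noncompliance selects patients on something that happens after randomization. Section VII lists adverse events "reported more frequently during use of pramipexole in restless legs syndrome patients than under placebo: nausea and fatigue", so missed doses, and removals that follow from them, could differ between arms. They could also follow from lack of effect, which might be more common on placebo. Either way, the t-tests would compare those not removed and not everyone randomized, although the analysis is labelled ITT.

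The payment rule points the same way. A patient who stops drug cannot earn the bonus however many diaries are completed, and so loses part of the reason to keep reporting. What is at stake is the meaning of the primary and key secondary t-tests as estimates of the effect of assignment.

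**Working it through.** **1. Who drops out of which test.** In the Table of Procedures, IRLS and SOWS fall on Days 1, 3, 5, 7, 9 and 10 of treatment.
- Removed after Day 3 and before Day 5: in the ITT set (dose taken, Days 1 and 3 assessed), but in neither t-test.
- Removed after Day 5 and before Day 10: in the Day 5 test only.
- In both cases the mixed models use the values recorded before removal and see nothing after it.

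**2. The plan's own power figure.** Inputs from section IX, Power/Sample Size: 34 per arm, difference 6.3, SD 9.0, two-sided alpha 0.05. Exact two-sample t power is 81.2%, which agrees with the stated 80%. The plan randomizes 88 to obtain 68 completers, an allowance of 20/88 = 22.7% for loss from any cause. Removals therefore threaten power only if total loss exceeds about 20 patients; the issue here is bias.

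**3. Size of a possible bias (assumed fractions; the documents give no removal rate).** Suppose a fraction p of the drug arm stops, loses all benefit and is removed, with no such loss on placebo. The effect of assignment is 6.3 × (1 − p), while the t-test on those remaining estimates 6.3. The overstatement is 6.3 × p, or p/(1 − p) in relative terms.

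| p | points | relative |
|---|---|---|
| 5% | 0.32 | 0.05/0.95 = 5% |
| 10% | 0.63 | 0.10/0.90 = 11% |
| 20% | 1.26 | 0.20/0.80 = 25% |

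The standard error of the difference is 9.0 × √(2/34) = 2.18 at 34 per arm and 9.0 × √(2/44) = 1.92 at 44 per arm, so each of these lies within sampling error. A milder assumption, with 10 to 20% removed who would have changed 2 to 5 points less than the rest, gives 0.10 × 2 = 0.2 to 0.20 × 5 = 1.0 points.

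The sign can reverse. If 10% of placebo patients, who would have improved 6.3 points less than the others, are removed, the effect is understated by 0.10 × 6.3 = 0.63.

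**4. Power if stoppers are kept.** Exact t, SD 9.0 held fixed, off-drug patients assumed to lose all benefit, 34 per arm with Day 10 values before any removal.

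| Stoppers in drug arm | kept: difference, power | removed: n, power |
|---|---|---|
| none | 6.3, 81% | – |
| 10% | 5.67, 73% | 30.6 v 34, 79% |
| 20% | 5.04, 62% | 27.2 v 34, 76% |

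**5. Payment.** The maximum is 10 × $5 + $25 = $75. If the daily $5 continues off drug, a patient who stops drug but completes every diary forgoes 25/75 = 33%.

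**The case against.** The case against giving this much weight is substantial. Removal is optional and is decided by blinded investigators. A code break is allowed only when treatment depends on knowing the arm. Site staff hand each nightly dose to inpatients for 10 days, and the dose rises only if well tolerated. The route from nausea to removal has several unproven steps, and section VII notes that some side effects overlap with withdrawal symptoms. The mixed models, listed as item (ii) of the primary analysis, keep pre-removal values. Early discharge from the CSS may well cause more missing data than removal does. All of this stands, and it limits the likely size. None of it supplies a Day 5 or Day 10 value for a removed patient.

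A reader might infer more than the documents support:
- *That any patient who misses doses goes unassessed.* Questionnaires are scheduled by study day, so a patient who misses doses and is not removed is still assessed. The loss comes from the removal wording.
- *That the drug effect is inflated.* The direction is unknown, as step 3 shows.
- *That the allowance of 20 losses measures removals.* It is pooled over arms and covers every cause; nothing supports placing it in one arm.
- *That all payment stops with the drug.* The daily $5 can be read as covering the 10-day treatment period; only the $25 is clearly conditional on time on drug. No document shows that it changes reporting.
- *That adverse event reporting is cut short.* Section VII sets its own reporting window, to 30 days after the last dose, and the point does not extend to it.

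**Conclusion.** The point holds as a limited one. As written, the removal rule lets post-randomization behavior decide who contributes to the ITT t-tests, for SOWS as well as IRLS, and the completion bonus leans the same way. The exposed group is probably small, and the documents give no removal or code-break rate by arm, so neither size nor direction can be stated. The illustrative 0.3 to 1.3 points rest on three assumptions: every stopper loses all benefit, every stopper is removed, and placebo has no offsetting loss. They also use 6.3 points, which the power section states for the IRLS scale and which may not carry over to the five-item, 24-hour subscale used here. The case for change is that the selection is avoidable at low cost, not that a large bias has been shown.

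**What to change.** Replace the noncompliance sentence with:

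> A participant who misses doses or stops study drug remains in the study; scheduled IRLS, SOWS, diaries and Visit 5 continue to Day 10 while the participant is in the CSS, unless consent is withdrawn.

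Then:
- Include these values in the ITT t-tests and mixed models, as randomized.
- After a code break, continue collection, and choose in advance whether those self-reports enter the main or a sensitivity analysis. They are open to bias on a subjective endpoint, so either choice is defensible if fixed beforehand.
- Base the $25 on completed diaries and questionnaires, not on days on drug.
- Report past removals by arm, with reasons.

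Residents already have the means to continue: "The Gavin Foundation CSS will be provided with a computer that will be used for questionnaires and study visits". No visits are added and the $75 maximum is unchanged.

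The costs are an amendment with revised consent wording, a few more bonuses, and the power loss in step 4 if off-drug patients lose all benefit. The higher power with removal belongs to a comparison of those not removed, not to the effect of assignment. The change also comes late. The Note in section IX reports 35 patients already randomized, so it reaches at most 88 − 35 = 53 of 88 (60%), or 68 − 35 = 33 by the target in that Note, and none if the interim analysis closes the study. Two follow-up rules would be mixed, which the report must state. The account of past removals is useful in every case. The fix does not supply the missing-data rule that the t-tests still lack for patients who leave the CSS early.

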Exploratory Aims:

- To determine whether pramipexole will have significantly greater effect than placebo for self-reported sleep metrics (e.g., quality, disturbance, sleep latency and duration) in OUD patients immediately following acute opioid withdrawal during post-detox clinical stabilization.
- To determine whether OUD patients on pramipexole will stay in the post-detox clinical stabilization unit longer than those on placebo. This will enable a higher rate of successful referral to after-care than those on placebo.

III. SUBJECT SELECTION

The following lists the inclusion/exclusion criteria for prospective participants.

Inclusion Criteria:

- 1. Men or women of any ethnic origin.
- 2. Written informed consent is obtained
- 3. Speaks and writes in English
- 4. A willingness and ability to comply with study procedures.
- 5. Age 18–75 years

- 6. Patients with diagnosed OUD who have undergone primary detoxification for their OUD in any detox facility, have been transferred to the Gavin Clinical Stabilization Service (CSS), and have some persistent opioid withdrawal as indicated by a SOWS>1 on Day 1
- 7. Diagnosis of RLS from the Hening Telephone Diagnostic Interview (HTDI) with subsequent confirmation by clinical interview conducted by a study physician (e.g., [name], [name])
- 8. International Restless Legs Syndrome Severity Scale (IRLS) Symptoms subscale score of >11 for three consecutive days prior to randomization. Participants who miss one day of questionnaires prior to randomization may be included if the IRLS subscale score is >11 for each day questionnaires are completed.

Exclusion Criteria:

- 1. Pregnant. Gavin Foundation staff perform pregnancy tests upon admission to the CSS.
- 2. Participants with active or unstable major psychiatric disorder other than OUD, who, in the investigators' judgement, require further treatment
- 3. Neurological disorder or cardiovascular disease raising safety concerns about use of pramipexole and/or judged to interfere with ability to assess efficacy of the treatment
- 4. Medical instability considered to interfere with study procedures
- 5. Stage 3, 4, or 5 renal insufficiency
- 6. Participation in this study on a previous admission to the CSS

IV. SUBJECT RECRUITMENT AND ENROLLMENT

Methods of recruitment and procedures for informed consent:

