The key secondary variables are the difference from randomization to Day 5 and from randomization to Day 10 in SOWS.

Exploratory analyses will similarly focus on the differences from randomization to Day 5 and from randomization to Day 10. These endpoints include:

- 1. Subjective total sleep time
- 2. Subjective sleep latency
- 3. Subjective time awake after sleep onset
- 4. Depressive (PHQ-9) and anxiety (GAD-7) symptoms
- 5. Time spent in the Gavin CSS

STATISTICAL METHODS

Interim analysis:

(i) Two-sample t-tests will be applied to estimate the effect of randomized treatment group on IRLS subscale score, for the subjects with post-randomization data to date. Using the estimated treatment effect, we will conduct a power analysis to determine the sample size necessary to detect this effect. (i) Two-sample t-tests will be applied to estimate the effect of randomized treatment group on SOWS, for the subjects with post-randomization data to date. Using the estimated treatment effect, we will conduct a power analysis to determine the sample size necessary to detect this effect.

Primary analysis:

(i) Two-sample t-tests will be applied to compare the change in IRLS subscale from randomization to Day 5 and from randomization to Day 10 between the two groups. (ii) Linear mixed-effects models will also be applied to the longitudinally measured IRLS subscale with entry of covariates that correlate with changes in primary endpoints as required (e.g., age, sex, and at-randomization levels of IRLS severity, and SOWS). Subjective sleep measures from the sleep diary for every night of data collection will also be added as potential covariates to the linear mixed-effects models.

Secondary Analysis:

(i) Two-sample t-tests will be applied to compare the change in SOWS from baseline to Day 5 and to Day 10 between the two groups. (ii) Linear mixed-effects models will also be applied to longitudinally measured SOWS with entry of covariates that correlate with changes in primary endpoints as required (e.g., age, sex, and at-randomization levels of IRLS severity, and SOWS).

Subjective sleep measures on every night of data collection will also be added as potential covariates to the linear mixed-effects models.

Exploratory Analyses:

Linear and generalized linear mixed-effects models will be applied to compare changes in the self-reported sleep metrics (e.g., quality, disturbance, sleep latency and duration) across the nights of study and between the groups.

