Linear and generalized linear mixed-effects models and survival-based analyses will be applied to compare the number of days patients continue in CSS treatment between the two groups.

Power/Sample Size:

Power calculations are based on Specific Aims 1 and 2 detailed below. There are insufficient published or unpublished data to perform them on exploratory analyses (detailed above). Meta-analyses of RLS clinical trials indicate that placebo effects using the IRLS are strongly related to the duration of these trials (Fulda et al., 2008). Therefore, we are basing our calculations on short-term trials, similar to our study design, for pramipexole in RLS using abbreviated RLS symptom scales (e.g., Oertel et al., 2007; Manconi et al., 2007, 2012)

Aim 1: The primary outcome is the change in IRLS scale from baseline to Day 10. Using the Oertel et al. (2007) data as reference, with n=34 for each group, we will have 80% power to detect a 6.3 points difference in the change of IRLS scale (with a common standard deviation of the change of 9.0) with a two-sided two-sample t-test at alpha=0.05 level. A change of 3 is considered a clinically meaningful difference from placebo (Allen et al., 2013).

Aim 2: The primary outcome is the change in SOWS. Using the Dunn et al. (2017) data as reference, with n=34, we will have 80% power to detect a 4 points difference in the change of SOWS (with a common standard deviation of the change of 6.0) with a two-sided two-sample t-test at alpha=0.05 level.

Therefore, our plan is to enroll 160 people in a 1:1 drug:placebo ratio in order to randomize 88 patients with OUD and have 68 participants complete the 10-day trial. With approximately 16 patients per week admitted to the CSS with opioid use disorder, and an RLS prevalence of 50% in this context, we do not anticipate any difficulty enrolling to our target sample size for the trial within a 20-month enrollment period.

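### Time in the stabilization unit has no analysis set of its own, and both defined sets require post-randomization data, so by inference the very shortest stays are left out

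*Combined protocol and SAP*

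**What the plan says.** Section IX, Overview of analytic plan, announces two kinds of analysis. The ITT set is described as "including all patients who received one dose of study medication and complete one assessment post-randomization". The other is given as "per protocol analyses (including participants with 10 days of evaluable data", where the parenthesis closes. No third set is defined.

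Retention appears in three places. Section II, Exploratory Aims: "To determine whether OUD patients on pramipexole will stay in the post-detox clinical stabilization unit longer than those on placebo". Section IX, Study endpoints, exploratory item 5: "Time spent in the Gavin CSS". Statistical Methods, Exploratory Analyses: mixed-effects models, and "survival-based analyses will be applied to compare the number of days patients continue in CSS treatment between the two groups". None of these names an analysis population or says from which day the stay is counted.

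Three other places fix the timing. The dispensing schedule in Section VI starts on Day 0, with dosing at about 6 p.m. The Table of Procedures puts the first IRLS, SOWS, craving scale and sleep diary after randomization on Day 1. Section V says that staff will try to hold Visit 5 before a patient who is discharged early leaves.

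For numbers, Power/Sample Size plans "in order to randomize 88 patients with OUD and have 68 participants complete the 10-day trial".

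**The concern.** For a questionnaire outcome, requiring one completed questionnaire is a common, if imperfect, restriction, because without it there is nothing to analyse. Length of stay is different. It can be measured in a patient who never fills in a form, and a patient who leaves on the first evening has the shortest stay possible. If the same set is used, being counted depends partly on the outcome being compared.

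The plan itself gives reasons why early departures might differ by arm. Section I argues that unrecognized restlessness may lead to relapse among patients in detox, and that treating RLS will lengthen stay. Section VII lists nausea and fatigue as more frequent on pramipexole than on placebo. Early departures on placebo, if dropped, would hide a benefit. Early departures on pramipexole, if dropped, would flatter the drug. In either case the contrast would no longer compare the groups as randomized.

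**Working it through.** **1. The plan's own numbers.** With a difference of 6.3, an SD of 9.0, two-sided alpha 0.05 and 80% power, the two-sample t-test needs 33.02 per group, which rounds up to the plan's 34. Power at 34 is 0.81. Two groups give 68 completers. The implied non-completion is (88 − 68)/88 = 20/88 = 22.7%, and 68/(1 − 0.227) = 88. These figures reproduce and are not in dispute. The plan gives no power calculation for the exploratory endpoints.

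**2. Who falls outside both sets.** Dosing is on the evening of Day 0 and the first forms are due on Day 1. Those excluded are patients who are randomized but never dosed, and patients who are dosed but leave with nothing completed. Anyone who completes one assessment on Day 1 and leaves later that day stays in the ITT set.

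**3. How many.** The documents do not say. Assume that all 20 non-completers leave the unit and that the daily risk of leaving is constant over 10 days:

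- daily risk = 1 − (68/88)^(1/10) = 0.0255
- leaving in the first day = 88 × 0.0255 = 2.2 patients
- share of the 20 = 2.2/20 = 11%

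**4. Effect on a Day 10 proportion.** Assume 44 per arm, with 8 leaving on pramipexole and 12 on placebo, 20 in all. An excluded early leaver comes out of the denominator only.

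| Excluded | Pramipexole | Placebo | Difference (points) |
|---|---|---|---|
| none (all randomized) | 36/44 = 81.8% | 32/44 = 72.7% | 9.1 |
| one per arm | 36/43 = 83.7% | 32/43 = 74.4% | 9.3 |
| two, placebo only | 36/44 = 81.8% | 32/42 = 76.2% | 5.6 |
| two, pramipexole only | 36/42 = 85.7% | 32/44 = 72.7% | 13.0 |

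**5. Effect on mean stay, restricted to 10 days.** Assume 44 per arm, excluded patients leaving at half a day, and other departures spread evenly over Days 2 to 9. With 14 placebo and 6 pramipexole departures, excluding one placebo patient changes the difference from 0.93 to 0.75 days. Excluding two placebo patients and one pramipexole patient changes it from 0.93 to 0.76. With 10 departures per arm and one excluded from each, the difference stays at zero, but two events are lost.

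**6. Per-protocol set.** It keeps only patients with 10 days of data. In the illustration of step 4, Day 10 retention becomes 36/36 versus 32/32, a difference of 0 whatever the truth.

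**The case against.** The plan never says that retention will be analysed in the restricted set, or that the two sets apply to every outcome. A reader might infer a flat statement to that effect, but the text supports only this: two sets are defined, and retention is given neither of them nor one of its own. The objection is right that the use of the ITT set is an inference.

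The window is also narrow. The plan does not define what counts as an assessment. On Day 1 the Table of Procedures lists several questionnaires, the diary, adherence and a safety check, and Visit 5 is attempted at early discharge. On a broad reading, any one of these keeps the patient in. Patients have also come through a 3-day run-in with at most one missed day of questionnaires, which tends to filter out the least engaged. So a reader who concludes that the comparison loses most departures, or its decisive ones, goes too far: most early departures remain in the set.

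Non-completion is not the same as leaving the unit either. Section VI allows removal for noncompliance and withdrawal after a code break, and such patients may stay in the CSS. Treating 20 of 88 as departures is therefore an assumption, and the documents give no figure for how early departures split by arm.

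All of this limits the size of the problem. It does not remove it: Visit 5 at early discharge is only attempted, and no text puts a patient with no completed assessment back into the comparison.

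**Conclusion.** The concern holds as a gap in specification. Followed as written, the plan makes inclusion in the retention comparison depend on being dosed and staying long enough to be assessed. The number affected is probably small, about 2 of 20 under the constant-risk and all-leave assumptions. With one lost per arm the illustration hardly moves (9.3 against 9.1 points). With two lost from one arm it moves by 3.5 points down (9.1 to 5.6) or 3.9 points up (9.1 to 13.0). The arm split, the 36/44 and 32/44, and the timing of departures are all assumed, so neither the direction nor the size of any actual bias can be stated.

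For this endpoint the per-protocol set is the worse of the two, because it removes essentially everyone who leaves before Day 10.

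A reader might go on to doubt the IRLS or SOWS conclusions. This point gives no ground for that. It concerns one exploratory endpoint without a power calculation.

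**What to change.** In Section IX, state that time in the CSS is analysed in all randomized patients, by assigned arm, in days from randomization to departure from the unit. No dose or completed questionnaire should be required, and patients who stop the study but remain in the unit should be included. State that the per-protocol set is not used for this endpoint. Call the present ITT set 'modified ITT', keep it for the questionnaire outcomes, and report the number excluded from it by arm, with reasons.

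The cost is small but not nil. A departure date must be obtained from the unit for every randomized patient, including those who have stopped the study, and the Table of Procedures has no entry for it. That the unit records this date is an assumption to confirm. Sample size, visits and treatment do not change.
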